Data preprocessing for all resting state scans will proceed as follows: data will be re-referenced to the average of the two ear electrodes, band-pass filtered, removed of obvious non-brain (i.e. movement) artifacts, and epoched into 4 second segments. Following preprocessing, a fast fourier transform will be applied to each epoch. The resulting spectral information will then be averaged across epochs. This spectral information will then be exported to Matlab where it will be analyzed with custom scripts developed in our laboratory. Activity in the alpha frequency band (8-12hz) will serve as the primary frequency band of interest.

Interim Data Analysis

Following acquisition of five full data sets, preliminary analyses will occur to assess the primary study outcomes and provide an opportunity to modify the protocol if necessary.

Aim 1. To determine how the experience of innocuous and noxious stimulation affects alpha activity.

Date: 6/6/2018

Principal Investigator: [name].

Application Number: HP-00064214

First, to identify the potential mechanisms that may drive modulations of alpha frequency under painful conditions, we will compare both the acute pain and neuropathic-like pain state scans against the most temporally proximate innocuous state scans. Each pain state will be compared to the baseline scan directly preceding it, and the differences between acute pain and warm and neuropathic-like pain and warm will be compared.

Second, we will compare the spectral characteristics of acute pain and neuropathic-like pain in the alpha frequency band and determine the ability of alpha frequency measures distinguish these two pain states. Each pain state will be compared to the baseline scan directly preceding it, and the differences between acute pain and warm and neuropathic-like pain and warm will be compared.

Aim 2. To assess the test-retest reliability of the alpha frequency as an objective measure of pain in two different experimental pain states (acute and neuropathic-like).

Here, we will identify the degree to which alpha frequency under various pain states remains constant across this time. This will be accomplished by comparing the resting states, and the differences between them, across testing sessions. If alpha frequency observations remain stable, within an individual, across testing sessions, this will provide important evidence that alpha frequency, and how it shifts, may represent an individually based characteristic or biomarker.

19. Informed Consent Process

Process: Once participants have received the initial telephone screening and approval, as described above, they will be invited to participate in an experiment. The study date will be arranged and the participant will arrive on that date. Before any research procedures begin, the participant will receive the consent form and will be given an opportunity to read the forms and ask questions before agreeing or refusing to consent. If the participant refuses consent, they will not be enrolled in the study.

Who will obtain consent: A research team member will obtain consent.

Setting: Consent will be attained in a private testing room, where only the research team member and participant will be present.

Provisions for understanding: Before the participant signs the consent form, the research team member will ask the participant if he or she understands what he or she has read in the consent form and if he or she has any questions. The research team member will then proceed with the Evaluation to Sign Consent form (attached) consisting of several questions. Upon successful completion of this evaluation, the consent form can be signed.

20. References

Date: 6/6/2018

Principal Investigator: [name].

Application Number: HP-00064214

de Vries M, Wilder-Smith OHG, Jongsma MLA, van den Broeke EN, Arns M, van Goor H, van Rijn CM. Altered resting state EEG in chronic pancreatitis patients: toward a marker for chronic pain. *Journal of pain research*. 2013; 6: 815-824.

Garcia-Larrea L. The posterior insular-opercular region and the search of a primary cortex for pain. *Clinical neurophysiology*. 2012; 42(5): 299-313.

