Condition 3: neuropathic-like pain. A topical application of 10% capsaicin cream will be placed on the participant's left volar forearm and covered with a Tegaderm bandage. A 40°C thermode will be placed directly on top of the capsaicin, and incubation will occur for twenty minutes. 40°C is confirmed as a temperature below the participant's pain threshold at V0. A five minute resting state EEG session follows incubation.

Condition 4: return to baseline. Following completion of the acute pain and neuropathic-like pain conditions, an ice-pack will be placed directly over the recently stimulated skin. The icepack will be held in place for five minutes. Pain ratings will be assessed to ensure that pain reports return to baseline levels. Following five minutes of icepack application, the ice pack will be removed and the thermode placed on the skin at skin temperature.

5. Relevant prior experience and gaps in current knowledge

While a simple EEG-based test could provide a useful diagnostic tool for assessing pain objectively, no study to date has evaluated this potential in a systematic way. Here we propose to build on our ongoing work to develop a reliable and simple measure of pain.

6. Background, rationale, and significance, and supporting literature

Neurophysiological investigations of pain have suggested that peak alpha frequency might provide a means of objective pain assessment. In healthy subjects, increased peak alpha frequency is strongly correlated with pain self-reports after exposure to acute noxious heat (*Nir et al., 2010*). Conversely, chronic pain patients compared to healthy control display decreased peak alpha frequencies higher in alpha power (*Sarnthein et al., 2006*). Measures of peak alpha frequency also show a negative

Date: 6/6/2018

Principal Investigator: [name].

Application Number: HP-00064214

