Individuals who meet the inclusion criteria will be scheduled for Visit 0. Study enrollment occurs when a participant arrives at Visit 0. The first 60 participants will complete Visits 1 and 2, while the remaining participants will only complete Visit 2. Visit 1 occurs at least 3 weeks after Visit 0 and Visit 2 occurs at least 3 weeks after Visit 1.

Visit 0:

The following procedures and assessments will be conducted at Visit 0:

1. Obtain informed consent
2. Perform urine screening for toxicology (random selection)
3. Urine pregnancy test (females only)
4. Administer health history form and review eligibility criteria, complete and sign eligibility form
5. Administer questionnaires (STAI-T, STAI-S, SCQ, BDI, EHI, BIS-11)
6. Pain scale training on COVAS
7. Quantitative Sensory Testing (QST) thermal threshold/supra-threshold testing (see below for details)
8. Offset analgesia test (see below for details)
9. Administer post-pain questionnaires (PCS, SFMPQ)
10. Ice pack application – total of 5 minutes or until pain = 0 for 60 seconds
11. Capsaicin application and incubation
12. Brush allodynia test and flare mapping
13. Ice pack application – total of 5 minutes or until pain = 0 for 60 seconds
14. Payment form completion
15. Schedule Visit 1

Visit 1:

The following procedures and assessments will be conducted at Visit 1:

1. Perform urine screening for toxicology (random selection)
2. Urine pregnancy test (females only)
3. Review eligibility criteria, complete and sign eligibility form

Date: 6/6/2018

Principal Investigator: [name].

Application Number: HP-00064214

4. Administer questionnaires (STAI-T, STAI-S, SCQ, BDI, EHI, BIS-11)
5. Pain scale training on COVAS
6. EEG cap setup
7. Quantitative Sensory Testing (QST) thermal threshold/supra-threshold testing (see below for details)
8. Offset analgesia test (see below for details)
9. Ice pack application – total of 5 minutes or until pain = 0 for 60 seconds
10. Resting state EEG runs (acute series):
 - a. 1 minute eyes open resting state
 - b. 1 minute eyes closed resting state
 - c. Baseline-acute resting state – 5 minutes (baseline thermode on)
 - d. Painful-acute resting state – 5 minutes
 - e. Administer post-pain questionnaires (PCS, SFMPQ)
 - f. Ice pack application – total of 5 minutes or until pain = 0 for 60 seconds (no EEG recorded)
 - g. Acute-return baseline resting state – 5 minutes
11. 5 minute break
12. Resting state EEG runs (chronic series):

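### In every pain-minus-baseline contrast the innocuous scan starts sooner after ice removal (minimum 0 to 10 min) than its pain scan (minimum 5 to 35 min), with no stated washout

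*Combined protocol and SAP*

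**What the plan says.** - Section 4 describes the baseline as a resting state free of pain and stimulation, with the thermode at 32°C (Condition 1). Condition 4 puts ice on the skin that has just been stimulated, checks that pain ratings have returned to baseline, and continues: "Following five minutes of icepack application, the ice pack will be removed and the thermode placed on the skin at skin temperature".
- Section 9, Visits 1 and 2, gives the ice step as "Ice pack application – total of 5 minutes or until pain = 0 for 60 seconds". It appears at step 9 (after the offset analgesia test), at step 10f (after the acute pain scan) and again after the capsaicin pain scan. The step-9 ice pack appears only in section 9.
- After step 9 come "1 minute eyes open resting state" and "1 minute eyes closed resting state", then the acute baseline (10c) and the acute pain scan (10d). According to section 4, the two short runs define each person's alpha band.
- After the ice at 10f comes "Acute-return baseline resting state – 5 minutes" (10g), and only then step 11, "5 minute break".
- The capsaicin series opens with a baseline-chronic scan at Visit 2 (12a). Visit 1 lists no such scan.
- Section 18, Aim 1: "Each pain state will be compared to the baseline scan directly preceding it". Aim 2 compares resting states, and the differences between them, across sessions.
- The documents state no interval between ice removal and a baseline scan, no check of skin temperature, and no adjustment for icing.

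**The concern.** Aim 1 reads the difference between a pain scan and its baseline as the effect of pain on alpha activity. If the baseline is recorded while recently iced skin is re-warming and the pain scan is recorded later, the difference also contains whatever icing does to alpha. The only check after icing is a pain rating, which does not register a cold but painless sensation. The scan order is the same for everyone, so neither a larger sample nor averaging removes such an effect.

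Two further comparisons are exposed. Aim 1 sets the acute difference against the neuropathic-like difference, and their lags are unequal, so an icing effect need not cancel. Aim 2 compares sessions, and the neuropathic-like comparator has a different lag at Visit 1 than at Visit 2. For the 60 people planned for both visits, that is a systematic change of procedure inside a reliability estimate.

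**Working it through.** The plan gives no figure for time since icing, so there is none to reproduce.

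**Inputs** (section 9 step lists): eyes-open and eyes-closed runs, 1 min each; baseline, return and pain scans, 5 min each; break at step 11, 5 min; capsaicin incubation, 20 min in the step lists and 15 min in the EEG paragraph. Section 4 mentions brief rests between scans without a length; they are set to 0, so every lag is a minimum.

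**Formula:** lag = sum of the listed durations between the latest ice removal and the start of the scan. Each pain scan is paired with the innocuous scan immediately before it. At Visit 1 that makes 10g the comparator for capsaicin pain. Section 18 does not name the rekindle scan; it is included because the comparator rule covers every pain state.

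| Contrast | Baseline lag (min) | Pain-scan lag (min) | Gap (min) |
|---|---|---|---|
| Acute, both visits | 1+1 = 2 | 1+1+5 = 7 | 5 |
| Neuropathic-like, Visit 1 | 0 | 5+5+20 = 30 (25 with 15-min incubation) | 30 (25) |
| Neuropathic-like, Visit 2 | 5+5 = 10 | 5+5+5+20 = 35 (30) | 25 (20) |
| Rekindle, both visits | 0 | 5 | 5 |

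Within each pair both scans follow the same ice pack and the baseline comes first. Unquantified rests can lengthen the lags but cannot reverse the order.

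**How many contrasts use which comparator:** 60 people are planned for Visit 1 and all 120 for Visit 2, which gives 60 + 120 = 180 neuropathic-like contrasts, rekindle aside. Of these, 120/180 = 67% use the 10-minute comparator.

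**Illustration of size, on assumptions that are not in the documents:** skin at 10 to 20°C when the ice comes off (a deficit of 12 to 22°C against 32°C), first-order re-warming with a time constant of 1 to 3 min, and a deficit above 2°C counted as cooled.

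- Time until the deficit falls to 2°C = time constant × ln(deficit/2). From 1 × ln(6) = 1.8 min to 3 × ln(11) = 7.2 min.
- Scan 10g (0 to 5 min): 1.8/5 = 36% of the scan cooled, up to 100%. The rekindle comparator has the same lag and the same range.
- Scan 10c (2 to 7 min): 0% to 100%.
- Scan 12a (10 to 15 min): 0%. The worst-case deficit at its start is 22 × exp(−10/3) = 0.8°C.

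**The same arithmetic after the proposed change:** 10g would start at 5 min, and the cooled share falls to between 0% and (7.2 − 5)/5 = 44%. With a 5-minute wait after step 9, 10c would start at 7 min, and the share is at most (7.2 − 7)/5 = 4%. The lags of 12a and of the capsaicin pain scans do not change, because the break is moved and not added.

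**The case against.** A reader might infer that skin cooling is built into every contrast, that all comparators fall within 2 minutes of ice, or that the step-11 break protects no comparator. The documents do not support any of these.

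- At Visit 2 the comparator for capsaicin pain is 12a, at least 10 minutes after ice. The break supplies 5 of those minutes. Even the worst case above leaves under 1°C. This stands, and it covers two thirds of the planned neuropathic-like contrasts.
- No skin temperature after icing is given, a 32°C thermode is on the skin, and nothing in the documents shows that mild re-warming shifts peak alpha frequency. This stands: neither the size nor the direction of an effect is known, and the 0 to 100% range for 10c shows how little the illustration settles.
- The site iced at step 9 is not stated. The test before it uses forearm, face and neck, so the iced skin may not be under the thermode in 10c. This stands for 10c. It does not help 10g, because Condition 4 places the ice on the stimulated skin and then the thermode on the skin.
- Section 9 lets the ice come off early once pain has been zero for 60 seconds. This makes the exposure variable, not absent, and possibly longer in people whose pain persists.
- The only analysis with a power statement (section 17) is the correlation between pain and peak alpha frequency. A shift common to everyone would not change a between-person correlation. That is correct, but the Aim 1 contrasts and Aim 2 differences are within-person differences, which such a shift enters directly.
- The zero lag at Visit 1 arises because that visit lists no baseline-chronic scan. This is true, and it is why the two lists need reconciling as part of the remedy.

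**Conclusion.** The point holds as a design weakness that should be corrected. Time since icing is confounded with pain state in every contrast, by at least 5 min (acute, rekindle), 30 min (Visit 1 neuropathic-like) and 25 min (Visit 2 neuropathic-like), or 25 and 20 min for the last two with the shorter incubation. These gaps rest only on the listed run lengths and the comparator rule.

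Whether this biases the alpha contrasts is not established. Residual cooling, or a painless cold sensation, is a possible confounder of unknown size. It matters mainly for 10g as the Visit 1 comparator, for the rekindle comparator, and for 10c if the step-9 ice was on the thermode site. It is probably negligible for 12a. The two short runs that set the alpha band also fall within 2 minutes of the step-9 ice, if rests are ignored. The 0 against 10 min difference between visits enters Aim 2 whatever the cause. No planned analysis can separate these effects afterwards, which is the reason to deal with them by design.

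**What to change.** 1. At Visits 1 and 2, move the existing 5-minute break from step 11 to between 10f and 10g. This adds no time and leaves the lags of 12a and of the capsaicin pain scans as they are.
2. Add a wait of about 5 minutes between step 9 and the first EEG run. State which site is iced at step 9.
3. Record the time from ice removal to the start of each baseline and return scan, and report it by scan type and visit.
4. Reconcile the Visit 1 and Visit 2 step lists so that both visits use the same neuropathic-like comparator. Moving the break alone would leave 5 min at Visit 1 against 10 min at Visit 2. The 20- and 15-minute incubation figures must also be reconciled.
5. Do not rely on time since ice as a covariate. The schedule nearly fixes it by scan type, so it is almost collinear with condition and can adjust for little.
6. These changes leave the rekindle pair as it is, so report that contrast with its 0-minute comparator lag stated.

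The ice step itself is not altered. The cost is protocol wording, about 5 minutes more per EEG visit, and the loss of the rest break between the acute-return scan and the capsaicin series. By the illustration, up to 44% of 10g could still be affected, so the change reduces the problem without guaranteeing its removal.

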 - a. Capsaicin application and incubation (EEG recorded) – 20 minutes
 - b. Painful-chronic resting state – 5 minutes
 - c. Administer post-pain questionnaires (PCS, SFMPQ)
 - d. Ice pack application – total of 5 minutes or until pain = 0 for 60 seconds (no EEG recorded)
 - e. Acute-return baseline resting state – 5 minutes (baseline thermode on)
 - f. Rekindle. Painful-chronic resting state – 5 minutes
13. Capsaicin removal and brush allodynia test and flare mapping
14. EEG cap removal
15. Payment form completion
16. Schedule Visit 2

Visit 2:

The following procedures and assessments will be conducted at Visit 2:

1. Perform urine screening for toxicology (random selection)
2. Urine pregnancy test (females only)
3. Review eligibility criteria, complete and sign eligibility form
4. Administer questionnaires (STAI-T, STAI-S, SCQ, BDI, EHI, BIS-11)
5. Pain scale training on COVAS
6. EEG cap setup
7. Quantitative Sensory Testing (QST) thermal threshold/supra-threshold testing (see below for details)
8. Offset analgesia test (see below for details)
9. Ice pack application – total of 5 minutes or until pain = 0 for 60 seconds
10. Resting state EEG runs (acute series):
 - a. 1 minute eyes open resting state
 - b. 1 minute eyes closed resting state
 - c. Baseline-acute resting state – 5 minutes (baseline thermode on)
 - d. Painful-acute resting state – 5 minutes

Date: 6/6/2018

Principal Investigator: [name].

Application Number: HP-00064214

- e. Administer post-pain questionnaires (PCS, SFMPQ)
 - f. Ice pack application – total of 5 minutes or until pain = 0 for 60 seconds (no EEG recorded)
 - g. Acute-return baseline resting state – 5 minutes
11. 5 minute break
 12. Resting state EEG runs (chronic series):
 - a. Baseline-chronic resting state – 5 minutes (baseline thermode on)
 - b. Capsaicin application and incubation (EEG recorded) – 20 minutes
 - c. Painful-chronic resting state – 5 minutes
 - d. Administer post-pain questionnaires (PCS, SFMPQ)
 - e. Ice pack application – total of 5 minutes or until pain = 0 for 60 seconds (no EEG recorded)
 - f. Acute-return baseline resting state – 5 minutes (baseline thermode on)
 - g. Rekindle. Painful-chronic resting state – 5 minutes
 13. Capsaicin removal and brush allodynia test and flare mapping
 14. EEG cap removal
 15. Payment form completion

Quantitative Sensory Testing (QST)

All quantitative sensory testing will be performed on the face, arm, and neck.

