with at least 30 seconds between trials, and the thermode is moved to a different position on the forearm/face/neck for each trial. The T1 and T2 durations for the three trials are: 4s/5s, 7s/4s, 5s/6s. We will subsequently test for offset analgesia at each body site while a second stimulus is simultaneously applied to another body site. This will be done for the following combinations of body sites: arm/face, left arm/right arm. Participants will be instructed to rate the pain intensity at one of the two sites using the COVAS.

Test for Brush Allodynia. This test is performed last, after incubation at V0 and after rekindle at V1 and V2. The capsaicin cream and film cover are removed, and the arm area is cleaned with alcohol and the original 1 inch square site is marked. The area of secondary hyperalgesia on the participant's arm is measured with a foam paintbrush dragged at 1 cm per second along four linear paths arranged vertically and horizontally around the marked capsaicin site. Brush stimulation from each direction is started outside the hyperalgesic area, and continued towards the marked square until the participant reports a change in sensation ('burning', 'tenderness', 'pain'). The border is marked on the skin with a marker from each direction. Finally the flare outside the capsaicin site is traced on transparency paper.

EEG

The EEG session will last about 2 hours and will include the following runs: 1 minute open eyes resting state, 1 minute closed eyes resting state, 5 minutes run of baseline-acute resting state, 5 minute run of acute-painful resting state, 5 minute run of acute-return baseline resting state, 15 minute run of capsaicin cream incubation, , 5 minute run of chronic-painful resting state, and 5 minute run of chronic-return baseline resting state, 5 minute run of chronic-painful resting state (rekindle).

Urine Screening

Urine screening will be decided randomly, by allowing the participant to choose 1 of 10 envelopes that s/he opens to reveal his or her assignment. 9 of the envelopes contain a paper that says 'No' to indicate no urine test and 1 envelope contains a paper that says 'Yes' to indicate a urine test will be conducted. Urine samples will be collected and immediately discarded after screening for drug toxicology. A urine sample for toxicology screening testing will be collected in a urine collection cup. The toxicology screening will be performed using Instant-View 12 Panel Drug Tests.

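### Visit 2 lists a pre-capsaicin baseline scan that Visit 1 lacks, probably a drafting inconsistency; if it is followed, the post-incubation difference may have a different reference scan at each visit

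*Combined protocol and SAP*

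**What the plan says.** Steps 10 and 11 of the two EEG visits in Section 9 are the same. Both acute series end with "g. Acute-return baseline resting state – 5 minutes", followed by a 5-minute break. Step 12 then differs. Visit 1 goes straight to "a. Capsaicin application and incubation (EEG recorded) – 20 minutes". Visit 2 has "Baseline-chronic resting state – 5 minutes (baseline thermode on" as step 12a and starts capsaicin at 12b.

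Two other places describe the sequence without a second pre-capsaicin baseline. Section 4 (Research design) gives baseline, acute pain, return from pain and neuropathic-like pain. The EEG paragraph of Section 9, which is not tied to a visit, runs "5 minute run of acute-return baseline resting state, 15 minute run of capsaicin cream incubation".

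Section 18 describes the reference scan under Aim 1 in three ways:
- Pain scans are set "against the most temporally proximate innocuous state scans".
- "Each pain state will be compared to the baseline scan directly preceding it".
- "the differences between acute pain and warm and neuropathic-like pain and warm will be compared".

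Aim 2 calls for "comparing the resting states, and the differences between them, across testing sessions" and does not say which reference forms those differences. Section 9 gives both EEG visits to the first 60 participants and only Visit 2 to the rest.

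**The concern.** Aim 2 would read a stable alpha shift as an individual characteristic or biomarker. That reading needs the shift to be measured in the same way at both sessions. If the reference for the post-incubation scan changes between visits, the retest mixes any change in the pain response with the difference between two kinds of reference scan. One follows acute heat and the ice pack directly; the other comes after a further scan and a break. An Aim 1 analysis that pooled Visit 1 and Visit 2 data would mix the two references as well. An Aim 1 analysis on Visit 2 alone would not, because the Visit 2 list is the same for everyone.

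**Working it through.** The plan gives no figure to reproduce, so the check sets the lists side by side, applies the Section 18 rule and adds up scheduled minutes. All times omit the brief rest periods mentioned in Section 4, whose length is not given.

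**1. Recorded runs**

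| Source | Runs | Minutes |
|---|---|---|
| Visit 1 | 9 | 1+1+5+5+5+20+5+5+5 = 52 |
| Visit 2 | 10 | 1+1+5+5+5+5+20+5+5+5 = 57 |
| EEG paragraph, Section 9 | 9 | 1+1+5+5+5+15+5+5+5 = 47 |

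The EEG paragraph matches Visit 1 run for run. Its 15-minute incubation contradicts the 20 minutes in the step lists and in Section 4. That is a separate discrepancy, also to be reconciled.

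**2. Reference under the preceding-baseline rule**

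| Pain scan | Visit 1 reference | Visit 2 reference | Same type? |
|---|---|---|---|
| Acute (10d) | 10c | 10c | yes |
| Post-incubation (12b / 12c) | 10g | 12a | no |
| Rekindle (12f / 12g) | 12e | 12f | yes |

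**3. Timing**

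- Start after the ice pack comes off: 10g at 0 min; Visit 2 step 12a at 5 (10g) + 5 (break) = 10 min.
- End of reference to start of post-incubation scan: Visit 1, 5 (break) + 20 (incubation) = 25 min; Visit 2, 20 min.
- With a 15-minute incubation these become 20 and 15 min; the 5-minute mismatch is unchanged.

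Condition 4 in Section 4 puts the thermode at skin temperature for the return scan, as at 12a. The two scans therefore differ in time since heat and ice and in the break, not in stimulus.

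**4. Other readings of Section 18**

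- Section 4 makes innocuous stimulation Condition 1 and return to baseline Condition 4. If only Condition 1 scans qualify, the Visit 1 reference is 10c. The gap is 5 (acute scan) + 5 (ice) + 5 (10g) + 5 (break) + 20 = 40 min plus questionnaire time (less if the ice pack comes off early), against 20 min at Visit 2. The references still differ.
- If closeness in time selects the return scan after the pain scan, the references are 12e at Visit 1 and 12f at Visit 2, which are like for like.

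**5. What a changed reference does**

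Let P be the post-incubation scan, G be 10g and B be Visit 2 step 12a; subscripts give the visit.

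(P1 − G1) − (P2 − B2) = [(P1 − G1) − (P2 − G2)] + (B2 − G2)

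The last term is not a change in pain response. If it is the same for everyone, it moves the mean session difference and any absolute-agreement measure, but leaves a correlation or a consistency-type ICC unchanged. If it varies between people, it also enters the correlation or ICC. Section 18 names no reliability statistic. The documents give neither the mean nor the SD of (B2 − G2).

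**The case against.** The strongest reply is that the extra scan is a drafting slip. Section 4 describes the sequence without it, the EEG paragraph omits it, and both visit lists call the return scan inside the chronic series an acute-return scan, which looks like copied text. If the scan is not meant to be there, and return scans count as baseline, 10g is the reference at both visits and nothing is wrong with the retest. This stands as the more likely explanation. It does not settle the matter, because the Visit 2 list is an explicit instruction and no text says which source governs.

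A second reply is that the rule is stated only under Aim 1. That is also right. A reader might infer that the plan prescribes mismatched references for Aim 2. It does not: Aim 2 names no reference, and carrying the rule over is an inference, though it is the plan's most explicit definition of such a difference.

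A third reply is that the identity is only algebra and shows no harm. Like-for-like references would still carry ordinary variation between G1 and G2, and nothing in the documents shows that replacing G2 with B2 makes the retest worse. This stands as far as size is concerned. What remains is that the comparator would change with the visit, for no stated reason.

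**Conclusion.** The step lists conflict with each other, and the Visit 2 list conflicts with Section 4 and the EEG paragraph. On two assumptions (the step lists are followed, and the Aim 1 preceding-baseline rule also forms the Aim 2 differences), the post-incubation neuropathic-like difference has reference 10g at Visit 1 and 12a at Visit 2, with scheduled gaps of 25 and 20 minutes. The consequence is limited to the retest of that one score in the first 60 participants and to any Aim 1 analysis that pools visits, which the plan does not say it will do.

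A reader might go further and conclude that the Aim 2 reliability results are biased or that data are lost. The documents do not support either. The size of (12a − 10g) cannot be computed from them and may be small; thermode temperature is the same; the raw scans and the acute and rekindle differences keep matching references; and Visit 2 as listed records both scans, so the term can be measured.

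**What to change.** First, reconcile Section 4, the two step lists and the EEG paragraph of Section 9 so that both visits record the same runs. Either choice works:
- Without the baseline-chronic scan, the reference is 10g and the scheduled gap is 25 min at both visits.
- With it at both visits, the reference is 12a and the gap is 20 min at both visits.

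Then name that scan by step number in Section 18 as the reference for the post-incubation difference in Aims 1 and 2, in place of the three present descriptions.

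The documents do not say whether any session has been run. If sessions have already followed the two different lists, use 10g, which is recorded at both visits, as the common reference and report (12a − 10g) at Visit 2 as a check. The gaps are then 25 min at Visit 1 and 5 (break) + 5 (12a) + 20 = 30 min at Visit 2. This aligns the type of scan but leaves a 5-minute mismatch in timing, so making the lists agree is the better remedy where it is still possible.

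The cost is a short edit to Sections 4, 9 and 18, and at most one 5-minute recording added or removed at one visit.
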